#### Paediatric population

Safety and efficacy have not been established for children and adolescents up to 18 years.

## Version 40 20/11/2014 REC Ref 12/SC/0592

#### 5.3 Preclinical safety data

Non-clinical data reveal no special hazard for humans based on conventional studies of safety pharmacology, single dose toxicity, phototoxicity, genotoxicity, carcinogenic potential and reproductive toxicity.

Effects observed in repeat-dose toxicity studies were mainly due to the exaggerated pharmacodynamic activity of rivaroxaban. In rats, increased IgG and IgA plasma levels were seen at clinically relevant exposure levels.

In rats, no effects on male or female fertility were seen. Animal studies have shown reproductive toxicity related to the pharmacological mode of action of rivaroxaban (e.g. haemorrhagic complications). Embryo-foetal toxicity (post-implantation loss, retarded/progressed ossification, hepatic multiple light coloured spots) and an increased incidence of common malformations as well as placental changes were observed at clinically relevant plasma concentrations. In the pre- and post-natal study in rats, reduced viability of the offspring was observed at doses that were toxic to the dams.

#### 6. Pharmaceutical particulars

6.1 List of excipients
Tablet core:

Microcrystalline cellulose

Croscarmellose sodium

Lactose monohydrate

Hypromellose

Sodium laurilsulfate

Magnesium stearate

Film-coat:

Macrogol 3350

Hypromellose

Titanium dioxide (E171)

Iron oxide red (E172)

## 6.2 Incompatibilities

Not applicable.

#### 6.3 Shelf life

3 years

#### 6.4 Special precautions for storage

This medicinal product does not require any special storage conditions.

### 6.5 Nature and contents of container

PP/Aluminium foil blisters in cartons of 14, 28 or 98 film-coated tablets or perforated unit dose blisters in cartons of 10 x 1 or 100 x 1 film-coated tablets.

Not all pack sizes may be marketed.

## 6.6 Special precautions for disposal and other handling

No special requirements for disposal.

## 7. Marketing authorisation holder

Bayer Pharma AG

13342 Berlin

Germany

## 8. Marketing authorisation number(s)

EU/1/08/472/017-021

#### 9. Date of first authorisation/renewal of the authorisation

Date of first authorisation: 30 September 2008

### 10. Date of revision of the text

05/2012

Detailed information on this medicinal product is available on the website of the European Medicines Agency http://www.ema.europa.eu.

Distributed in the United Kingdom by:

Bayer plc

[name]

[name]

Newbury

Berkshire

[name]

# Appendix 2. Rare Adverse Events which are Serious and a high Proportion are due to drug

Agranulocytosis

Alveolitis

Anaemia aplastic

Anaphylaxis

Angioneurotic oedema

Arrhythmia

Bone marrow abnormal

Congenital abnormality

Dermatitis exfoliative

Disseminated intravascular coagulation

Erythema multiforme

Erythroderma

Guillain-Barre syndrome

Hepatic failure

Hepatitis

Jaundice

Leucopenia

Multiorgan failure

Nephritis

Nephrotic syndrome

Neuroleptic malignant syndrome

Neutropenia

Pancreatitis

Pancytopenia

Pseudomembranous colitis

Renal failure acute

Retroperitoneal fibrosis

Rhabdomyolysis

Stevens Johnson syndrome

Sudden Unexpected Death

Thrombocytopenia

Torsades de pointe

Toxic epidermal necrolysis

Any event for which there is a positive rechallenge Version 40 20/11/2014 REC Ref 12/SC/0592

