The study also includes (for rivaroxaban cohort only) several exploratory analyses to 1) where possible, to quantify the incidence of other important identified ,potential and special risks and outcomes of interest (such as severe abnormal liver function) not mentioned in the primary objective, other frequently and rarely reported adverse events during treatment with rivaroxaban and to identify previously unrecognized adverse drug reactions for rivaroxaban; and 2) describe clinical features and management of cases of overdose, major bleeding, VTE events indicating failure of anticoagulation and management of homeostasis in patients undergoing surgery (elective or urgent) during observation of the cohort exposed to rivaroxaban.

<sup>‡ The term 'event', as used in this study, is defined as, "any new diagnosis, any reason for referral to a consultant or admission to hospital, any unexpected deterioration (or improvement) in a concurrent illness, any alteration of clinical importance in laboratory values, or any other complaint that was considered of sufficient importance to enter in the patient's medical charts."

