- Medical history relevant for important potential, identified and special risks of interest (plus dates of first diagnosis/report). For example: past history of DVT/PE, myocardial infarction (MI), percutaneous coronary intervention (PCI), coronary artery bypass graft (CABG), other recent surgery within 3 months prior to index date, malignancy, pregnancy, family and/or personal history of congestive heart failure, diabetes mellitus, hypercholesterolaemia, peripheral arterial disease, COPD etc.)
- Specific information on renal function status at index date and any changes during 12 week observation period
- Specific information on hepatic disorders present at index date (cholestasis and jaundice, hepatic failure and associated disorders, hepatic fibrosis and cirrhosis and hepatic viral infections) and any recent abnormal liver function tests.

Version 40 20/11/2014 REC Ref 12/SC/0592

##### for rivaroxaban only

- event reports including selected risks of interest (Table 4)
- o cause and date of death (if died) in the first 12 weeks after starting treatment;
- reported pregnancies at start or during the first 12 weeks after starting treatment and outcome of birth.
- behaviours prior to and/or starting treatment (e.g. smoking, alcohol/substance misuse); treatment adherence

Risk/Missing Information	Proposed data capture	Comment
IDENTIFIED, POTENTIAL AND SPECIAL RISKS A	ND OUTCOMES for targeted data	collection on SCEM questionnaires
Major bleeding episode (into a critical organ	Targeted outcome questions on	Selected risk factors collected on SCEM
sites )	critical sites	questionnaire. Further data on severity,
		management and risk factors to be collected
		via follow-up.
Clinically relevant minor bleeding episodes	Targeted outcome question to	Selected risk factors collected on SCEM
	specify details	questionnaire. Not for follow-up
Incident and recurrent thromboembolic	Targeted outcome questions	Selected risk factors collected on SCEM
complications (DVT, PE, Stroke)		questionnaire. Further data on symptoms,
		severity, management and risk factors to be
		collected via follow-up.
Overdose. accidental trauma and Reversal of	Targeted outcome question	Events of overdose (dose > 50mg/day) and
anticoagulation therapy		accidental trauma are those of clinical
		medical importance which require acute
		medical/surgical treatment (with or without)
		hospitalisation Further data to be collected
	-	via follow-up

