## 4.4.2.4 Abridged 12 week end of observation questionnaire for GP

For each evaluable patient recorded as having been discharged from under the care of the specialist HCP to the care of their GP during the 12 week observation period, their GP will be contacted and invited to complete an abridged end of observation SCEM questionnaire which will gather information on clinical events of medical interest and serious adverse event reports [classified using the International Conference on Harmonisation definitions [36]] reported since date of discharge from secondary care up to end of the 12 week observation period, and recorded within primary care medical charts. Data obtained from this abridged 12 week SCEM questionnaire will include:

- o Anticoagulant treatment regimen as prescribed in primary care
- event reports of selected risks of interest (Table 4)
- cause and date of death (if died);
- reported pregnancies and outcome of birth.
- o date and reasons for stopping (if stopped) including switching
- any newly prescribed concomitant treatments

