- 4. Adverse events: Other adverse events deemed of medical importance by the DSRU which are considered to be possible safety signals (either arising from literature reports post marketing, or subsequent to interim data analysis) may also be followed-up for additional information on relevant risk factors for signal strengthening purposes.
- 5. Adverse events: Events within the list of Rare and Iatrogenic Adverse Reactions (RAIDAR) compiled by the DSRU (Appendix 2) will be automatically followed up if a more likely alternative explanation for their occurrence is not given.

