# Total number of new cases during 12 week observation period x 100 Population initially at risk

If the observed cumulative incidence from the SCEM study falls within the range expected as set by the precision limits of cumulative incidence from clinical trial data, then the null hypothesis (of no difference) will not be rejected. Cumulative hazard rate methods account for truncation of exposure time and censoring; for these analyses the exposure time would be censored at the time of the first event. Kaplan-Meier plots will be presented to describe timeto event as well as smoothed hazard plots to describe how the baseline risk of an event changes over time. Estimates of the hazard function will also be modelled to determine whether the baseline hazard (risk) of the event increases or decreases with time. A constant hazard over time may be consistent with a background (not caused by the drug) event rate, whereas a non-constant hazard over time may be an indicator of a drug-event relationship. The null hypothesis that the hazard rate of the selected event in patients prescribed rivaroxaban will be constant during the 12 week period following the start of treatment will be tested by fitting a parametric time to event model (e.g. Weibull). Such models have a shape parameter that indicates whether the hazard is significantly increasing or decreasing over time. At least five reports of an event are deemed necessary for modelling purposes.\*\*\*\*\*\*

Several sensitivity analyses will be performed: In one, observation start date will be imputed to be the same as the diagnosis date (i.e the index date will be shifted backwards in time) for those patients for whom a lag period between diagnosis and receiving rivaroxaban treatment was reported. The application of time-varying covariates methodology will enable examination of the impact of any transition from other treatments given as part of initial standard care on the results. In addition, since the primary analysis will be run only to include confirmed cases of incident major bleeding, it will be necessary to explore the reasons for exclusion of incomplete cases and examine their impact on the estimated measure of frequency.

Where possible, data will be stratified according to relevant strong risk factors (e.g. gender, age ( $\leq 60, 60-74, \geq 75$  years), indication and past history of haemorrhage or VTE) and stratum-specific incidence rates examined.

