Calculating and ranking crude ID rates is one of a number of standard quantitative evaluations used in event monitoring methodology for signal generation purposes as part of initial inspection of all event data for general safety surveillance. It is used as a means of alerting early potential signals as priorities for further evaluation. Medical judgment however is also part of this evaluation and prioritization process. Crude Incidence Densities (ID) ‡‡‡‡‡‡ can be calculated by week in order to quantify rates of events. IDs will be calculated, for each given time period (t), for all events reported in patients who continue to take rivaroxaban for a given time period, or for whom the date of stopping is known. Only the first report of an event in an individual patient is used in the calculation of IDs. They are usually expressed as the number of first reports of an event per 1000 patient-weeks. This assumes the pattern of use is continuous. The numerator will be the first reports of events reported as occurring after the index date and during treatment.§§§§§§§ For this study, IDs will be calculated for each event for each week as follows:

$ID_t =$	Number of first reports of an event during treatment for period t x 1000					
	Number of patient-weeks of treatment for period t					
Thus,	$ID_t =$	Nt x 1000				
		Dt				
where:	$N_t =$	Number of first reports of an event during treatment for period t,				
and	$D_t =$	Number of patient-days of treatment for period t / 7				

IDs will also be calculated for each event for all 12 weeks during treatment combined (IDA), and the first week after stopping (IDSW1) if patient stopped (and where patients are recorded as remaining on treatment for at least 1 week) after index date.

<sup>‡‡‡‡‡‡‡ It should be noted such quantification of rate does not only reflect the rate attributable to the drug but also reflects the background rate in the general population and rate attributable to other factors such as age or other disease risk factors

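### Non-serious events outside Table 4 are not itemised on the GP form, yet their incidence densities keep the treatment weeks after discharge, so those rates are biased low

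*Supplement*

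**What the plan says.** The Executive Summary defines an event widely. The definition extends to "any other complaint that was considered of sufficient importance to enter in the patient's medical charts", whether serious or not. Section 2.2.2 (iv)(f) sets out to quantify such other events over 12 weeks, and Section 2.2.3 (i) to find unrecognised reactions.

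Two forms supply the events:

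- **Specialist form (4.4.2.3).** It collects "event reports including selected risks of interest (Table 4", so Table 4 is a subset of what is asked. It also asks for blood results, and abnormal values are to be reported as events.
- **GP form (4.4.2.4), for patients discharged during the 12 weeks.** The opening sentence says it will "gather information on clinical events of medical interest and serious adverse event reports" from discharge to week 12. The itemised list then gives "event reports of selected risks of interest (Table 4", together with treatment regimen, death, pregnancy, stopping and new co-medication. It has no open event item and no laboratory item.

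Section 4.1 expects shared care for most patients and presents the GP contact as a means of limiting under-reporting of selected outcomes.

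Section 4.7.5 calculates incidence densities for all events, by week and for the 12 weeks combined. The denominator is "Number of patient-weeks of treatment for period t", with no cut at discharge. The sensitivity analysis using primary care records adds only events of interest.

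Section 4.7.5 also allows Weibull models for events of interest with at least five reports. Section 4.7.2 gives the reading of such models: "a non-constant hazard over time may be an indicator of a drug-event relationship".

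Appendix 2 (the RAIDAR list) is headed "Rare Adverse Events which are Serious and a high Proportion are due to drug". Under Section 4.4.2.5, item 5, events on it "will be automatically followed up if a more likely alternative explanation for their occurrence is not given".

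**The concern.** The numerator and denominator of the incidence density cover different periods for one class of event: non-serious events outside Table 4. Before discharge the specialist is asked for them. After discharge nobody is clearly asked, but the patient's treatment weeks continue to count. Two things follow.

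- The 12-week rate is too low, which weakens the general surveillance for which these densities are computed.
- The captured fraction falls as patients are discharged. A truly constant hazard then appears to decrease, and the plan treats a non-constant hazard as a possible signal. This second effect needs the event to have been chosen for Weibull modelling.

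The gap lies in what the form asks, so a complete return of GP forms would not close it.

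**Working it through.** **The plan's own figure.** Section 4.2.2 states that 1700 patients give 99% probability of at least three cases at a rate of 1 in 200. The exact binomial P(X ≥ 3) with n = 1700 and p = 1/200 is 99.1%, so the figure reproduces. The expected number of cases is 1700/200 = 8.5. The calculation presumes that every case over 12 weeks is captured.

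**Model.** True hazard constant over 12 weeks; all patients treated throughout; share π discharged at week d; fraction m of post-discharge events not captured. The documents give none of π, d or m, so the values below are assumptions chosen to show the range.

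**Rate.** Captured over true incidence density = 1 − m·π·(12 − d)/12.

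- m = 1, π = 0.25, d = 8: 1 − 0.25 × 4/12 = 0.92
- m = 1, π = 0.90, d = 2: 1 − 0.90 × 10/12 = 0.25

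**Weibull shape.** For rare events followed to week 12, the fitted shape tends to k = 1/(ln 12 − mean ln t), where the mean is over captured event times. Captured events have relative density 1 up to week d and 1 − mπ afterwards.

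For m = 1, π = 0.90, d = 2:

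- The integral of ln t is 2 ln 2 − 2 = −0.614 over weeks 0 to 2, and 17.819 + 0.614 = 18.433 over weeks 2 to 12.
- Mean ln t = (−0.614 + 0.1 × 18.433)/(2 + 0.1 × 10) = 0.410.
- k = 1/(2.485 − 0.410) = 0.48.

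**Detection.** The binomial calculation is repeated with p multiplied by the rate ratio.

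| m | π | d (weeks) | Rate, captured/true | Weibull shape | P(at least 3 captured), true rate 1/200 |
|---|---|---|---|---|---|
| 1 | 25% | 8 | 0.92 | 0.93 | 98.4% |
| 1 | 50% | 4 | 0.67 | 0.78 | 92.2% |
| 1 | 75% | 4 | 0.50 | 0.65 | 79.7% |
| 1 | 90% | 2 | 0.25 | 0.48 | 35.7% |
| 0.5 | 50% | 4 | 0.83 | 0.90 | 97.2% |

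**Checks on the mechanism.** With m = 0 (the event type is requested and fully reported) the rate ratio and shape are both 1.00. If person-time ends at discharge, the shape is again 1.00 and, under a constant hazard, the rate is unbiased. The distortion therefore comes from keeping time during which the event is not asked for.

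**The case against.** The strongest reply is that the contrast rests on thin wording: *including* in one bullet and *of* in the other. Both forms are introduced with nearly the same scope phrase, the GP list is not worded as exhaustive, and neither form is shown. Events of medical interest is undefined and could be read to cover everything. This lowers certainty about what the GP is actually asked. Against it, the GP form is called abridged, has no laboratory item, and is justified in Section 4.1 by selected outcomes only. On the text as written, the narrow reading is the natural one.

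A second reply is that Section 4.1 shortens observation when a patient leaves specialist care, which would remove the bias. That is true if the rule governs the analysis. But Section 4.7.2 runs time to stopping plus two days or week 12, Section 4.7.5 counts all treatment weeks, and Section 4.4.2.4 collects data to week 12. The sections conflict.

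Third, total loss after discharge is an extreme assumption. Some later events may reach the hospital charts, and the m = 0.5 row shows a smaller effect. The densities are also described as crude screening measures that medical judgement supplements. These points limit the size of the bias but leave its direction unchanged.

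A reader might infer more: that the GP is asked only about Table 4, and that RAIDAR events after discharge are lost. The documents do not support this. Section 4.4.2.4 also requests serious adverse events, and the Appendix 2 heading calls its events serious. Hepatic failure and raised liver enzymes fall under Table 4 as well. At most, a mild case of a listed term, such as leucopenia, that the GP did not class as serious could be missed. Nor does automatic follow-up conflict with the GP form, since it applies to events already reported.

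**Conclusion.** The point holds for non-serious events outside Table 4. If Section 4.7.5 is followed as written, their incidence densities are biased low. Under total loss after discharge, the scenarios shown put the rate between 0.92 and 0.25 of its true value, and the chance of capturing three cases at 1 in 200 between 98.4% and 35.7%, against the 99% planned. Those figures rest on assumed discharge shares and weeks, a constant hazard and treatment throughout; the direction needs only that some patients are discharged while still treated and that some of their later events go unreported.

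The false fall in hazard (shape 0.93 to 0.48 in the same scenarios) is a narrower risk. It applies only to an event outside the GP's list that is taken up as an event of interest with at least five reports, and Section 4.7.2 treats a non-constant hazard as a possible indicator, not as proof.

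The primary bleeding outcomes are requested from the GP and are untouched by this gap, as are serious events. The matter concerns general safety surveillance and should be corrected, but it does not threaten the primary objective.

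**What to change.** Either of two changes removes the bias:

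1. In Section 4.4.2.4, give the GP form the same open question as the specialist form: any event since discharge. Cost: one more question on the GP form.
2. In Section 4.7.5, for event types the GP form does not request, end patient-weeks and time-to-event follow-up at discharge. Cost: analysis wording only, with fewer patient-weeks for general events.

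The first is preferable where it is still feasible, because it keeps the full 12 weeks of surveillance. In either case, reconcile the Section 4.1 rule on when observation ends with the time at risk in Sections 4.7.2 and 4.7.5, and define what counts as an event of medical interest on the GP form.
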